**MASCC Antiemesis Tool**  
This page asks about the period from the day after to 4 days after chemotherapy.  
So it asks about the time after the first 24 hours.

Please fill this out **four** days after chemotherapy on:

Day	Month	Day of the Week
		

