**STUDY SCHEMA**

**STUDY SUMMARY**

Title	Fixed-Dose Combination of Netupitant and Palonosetron (Akynzeo®) in the Treatment of Refractory Chemotherapy-Induced Nausea and Vomiting
Short Title	Akynzeo® in the Treatment of Refractory CINV
Phase	II
Methodology	Single-arm, single-center, open-label study
Study Duration	The anticipated total study duration is 24 months from fully-executed contract and IRB approval. Individual subject participation is limited to approximately 1 week.
Study Center(s)	UC San Diego (UCSD) Moores Cancer Center UCSD Medical Center - La Jolla
Objectives	
Primary: To determine the feasibility of using a fixed-dose combination of netupitant and palonosetron (Akynzeo®) in the treatment of refractory CINV. For this study, refractory CINV is defined as nausea and/or vomiting that occurs after the first cycle of cancer targeted therapy despite guideline-based prophylaxis and after first-line rescue medication with either a dopamine receptor antagonist, steroid, and/or benzodiazepine.
 
Hypothesis: Feasibility, defined as more than 70% of selected study subjects completing all study related procedures, will be achieved.
 
Secondary:
 
 
• To evaluate the occurrence of adverse events using the National Cancer Institute Common Terminology Criteria for Adverse Events (CTCAE) version 4.03.
 
• To evaluate complete response defined as no emesis and no use of rescue medication for 5 days after Akynzeo® administration.
 
• To characterize 24-hour intervals of CINV using the MASCC Antiemesis Tool (MAT).
 
• To evaluate 5-day health related quality of life recall using the Functional Living Index for Emesis (FLIE) scale.
 
• To evaluate healthcare resource utilization as defined by the number of emergency room visits, hospitalizations, and infusion center visits encounters regarding signs/symptoms associated with CINV over the seven-day study period.
 
• To evaluate the occurrence of refractory CINV using CINV risk assessment at follow up day 7 compared to treatment day 1.
 
 
Exploratory: To determine patient preference for use of Akynzeo® for future planned chemotherapy utilizing a five-point Likert scale

Number of Subjects	50

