**SCHEDULE OF EVENTS**

	Screening	Treatment (Study Day 1)	Follow-Up (Study Day 2-3) 	Follow-Up (Study Day 4-7) 
Informed consent	X			
Inclusion/exclusion criteria	X			
Demographics	X			
Medical and surgical history	X			
ECOG Performance Status	X			
Confirmed presence of refractory CINV	X			
Serum pregnancy test 	X			
Physical exam with vitals, weight 	X		per routine frequency	
Complete metabolic profile 	X		per routine frequency	
Complete blood count with differential, platelets 			per routine frequency	
EKG QTc evaluation	X 		X 	
Patient CINV risk factors		X		X
Akynzeo® dispensing and administration		X		
Patient medication diary		X		
Collect hospitalization and emergency room visit data		X	X	X
Concomitant medications	X	X	X	X
Adverse event monitoring		X	X	X
MASCC Antiemesis Tool  (MAT)	X	X	X	X
Functional Living Index for Emesis (FLIE) scale 	X	X		X 
Patient preference Likert-scale				X 

 Women of childbearing potential only

 Subjects will be monitored for a total of 6 days following Akynzeo® dosing

 QTc evaluation on Day 3±3 days with single EKG. If patient experiences worsening cardiac symptoms during the study, additional EKG(s) will be performed as clinically indicated

 Complete on Day 5 only

 Daily unless otherwise indicated. Daily safety assessment and hospitalization/ER visit information on Days 2-7 may occur via in-person visit or telephone call from a study team member. Subjects will also receive a daily reminder (via in-person visit or telephone call) to complete required questionnaires/diaries.

 Complete on Day 7 only

 EKG, laboratory and physical exam results obtained within 4 weeks prior to the informed consent date may be used to fulfill study requirements. EKG results may be obtained after screening processes yield positive refractory CINV.

 To be completed daily for 4 days after CINV prophylaxis or Akynzeo® dosing.

 To be completed on the 5th day after CINV prophylaxis or Akynzeo® dosing

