### **2.2 Secondary:**

- To evaluate the occurrence of adverse events using the National Cancer Institute Common Terminology Criteria for Adverse Events (CTCAE) version 4.03.10
- To evaluate complete response defined as no emesis and no use of rescue medication for 5 days after Akynzeo® administration.
- To characterize 24-hour CINV using a modified MASCC Antiemesis Tool (MAT). (**Appendix 1**)
- To evaluate 5-day health related quality of life recall using the Functional Living Index for Emesis (FLIE) scale.
- To evaluate healthcare resource utilization as defined by the number of emergency room visits, hospitalizations, and infusion center visits encounters regarding signs/symptoms associated with CINV over the seven-day study period.
- To evaluate the occurrence of refractory CINV using CINV risk assessment at follow up day 7 compared to treatment day 1.

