### **5.5.2 Multinational Association of Supportive Care in Cancer (MASCC) Antiemesis Tool® (MAT)**

The MAT is a validated tool to measure CINV in 24-hour intervals developed by members of Multinational Association for Supportive Care in Cancer (MASCC) to assist patients and oncology professionals in communicating accurately about the prevention and control of nausea and vomiting that may occur with chemotherapy. The concept of the MAT is to provide an easy-to-use and easy-to-evaluate tool to assist in providing the best individual care to patients. Additionally, the tool will aid treatment centers in understanding the effectiveness of their antiemetic strategies. The MAT was first created and posted in 2004. It is now available in eleven languages, obtained by the standard forward/backward translation process. The MAT consists of eight items. Four of these items refer to the occurrence, duration, and frequency of acute nausea and vomiting, and four refer to the occurrence, duration, and frequency of delayed

nausea and vomiting. Dichotomous items are scored “0” (“No”) or “1” (“Yes”) and continuous variables as marked on the 0-10 scale. In total, there are 4 dichotomous variable items and 4 continuous variable items. There is no summing of items; instead, items are evaluated on their own in clinical practice. Each subject will complete a written form of the MAT at approximately the same time each day during the study. The MAT will be completed daily for 4 days after CINV prophylaxis and after Akynzeo® treatment (Study Day 1). Thereafter, it will be completed daily during the post-treatment observation portion of the study at the same time each day starting 24 hours from the time of previous questionnaire completion. English and Spanish versions of the MAT will be made available at study activation. Additional foreign translations will be performed as needed.

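### As printed, the MAT yields neither 24-hour intervals nor emesis over the 5 days after Akynzeo; no emesis source is named for complete response, and two count items are described as 0-10

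*Combined protocol and SAP*

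**What the plan says.** **Objectives.** The Study Summary sets the aim "To characterize 24-hour intervals of CINV using the MASCC Antiemesis Tool (MAT"). Section 2.2 sets "To evaluate complete response defined as no emesis and no use of rescue medication for 5 days after Akynzeo® administration" and "To characterize 24-hour CINV using a modified MASCC Antiemesis Tool (MAT"), and points to Appendix 1 for the modified tool.

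**Form.** Appendix 1 has two pages. Q1-Q4 cover the first 24 hours after chemotherapy. Q5-Q8 cover the rest on a single page, headed "This page asks about the period from the day after to 4 days after chemotherapy". Nothing on either page refers to Akynzeo.

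**Timing of completion.** Footnote 8 of the Schedule of Events reads "To be completed daily for 4 days after CINV prophylaxis or Akynzeo® dosing". Section 5.5.2 goes further: "Thereafter, it will be completed daily during the post-treatment observation portion of the study", at intervals "starting 24 hours from the time of previous questionnaire completion". The Schedule grid marks the MAT in the Day 4-7 column as well as on Days 2-3. Section 5.0 supplies questionnaire copies for Days 2-7, and section 5.1 has staff remind subjects about the MAT in the daily calls.

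**Analysis.** Section 9.3(2) names the two components of complete response and a z test against 90%, but gives no emesis source, time origin or window. Sections 5.5.2 and 9.3(3) describe four MAT items as binary and four as continuous on 0-10.

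**The concern.** The rescue half of complete response has a daily record, the medication diary of section 5.5.1. The emesis half has no designated record. The daily MAT is the likely intended source, but its printed questions run from a different time origin and merge several days into one answer. An analyst would have to choose the source and the window after the data are in.

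The error can go either way. Late post-dose vomiting that no form captures would raise the response rate. Vomiting before the dose that is merged into a chemotherapy-timed answer would lower it.

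Complete response is the secondary outcome tested against 90%, and section 5.3 would use the secondary results to look for an endpoint for the next trial. The item-type error separately affects how the MAT results in 9.3(3) are summarised.

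**Working it through.** **The plan's own figure.** The only computed design figure is 80% power for the primary aim (section 9.2). With a one-sided 0.05 test and the normal approximation it reproduces: Φ[(0.15 × √50 − 1.645 × √(0.7 × 0.3)) / √(0.85 × 0.15)] = Φ[(1.061 − 0.754) / 0.357] = Φ(0.86) = 80.5%. Nothing below enters that calculation.

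**Coverage if the printed form is completed once, as headed.** The endpoint window is 0-120 h after dosing. The delayed page ends 96 h after chemotherapy by the clock, or at about 120 h if counted to the end of the fourth calendar day.

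- Dosing on the day of chemotherapy (no lag): uncovered time is 120 − 96 = 24 h (24/120 = 20%), down to about 0 h on the calendar reading.
- Dosing d hours after chemotherapy, form counted to 96 h: uncovered time is min(d + 24, 120) h. The lag d is an assumption; the documents do not give it.

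| Assumed lag d | Uncovered | Share of 120 h |
|---|---|---|
| 0 h | 24 h | 20% |
| 24 h | 48 h | 40% |
| 48 h | 72 h | 60% |
| 72 h | 96 h | 80% |
| 96 h or more | 120 h | 100% |

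Section 7.0 mentions dosing on C2D1, while section 6.0 has dosing follow confirmation of refractory CINV on Day 1. These do not settle the lag.

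**Coverage if forms are completed daily, 24 h apart.**

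- Footnote 8: forms at 24, 48, 72 and 96 h. Four of the five intervals are closed; 96-120 h has no form.
- Section 5.5.2 and the grid (Days 2-7): forms at 24, 48, 72, 96, 120 and 144 h. All five intervals are closed, provided each form asks about the last 24 hours. The printed form does not.

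**Effect on complete response.** One subject of 50 is 1/50 = 2 percentage points. For the test against 90%, z = (x/50 − 0.9) / √(0.9 × 0.1/50), with denominator 0.0424:

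- 40/50: z = −2.36
- 41/50: z = −1.89
- 35/50 (an illustrative 70%): z = −4.71

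At a two-sided 0.05 level (assumed, since 9.3 states none for this test), one subject changes the result between 40 and 41 responders. The mirror boundary is between 49 and 50 (z = 1.89 and 2.36). Starting from 35/50, five subjects moved to response give 40/50, which still rejects.

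**Item types on the printed form.**

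| Type | Items | Number |
|---|---|---|
| Yes/no | Q1, Q3, Q5, Q7 | 4 |
| Open count | Q2, Q6 | 2 |
| 0-10 scale | Q4, Q8 | 2 |

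The form's own instructions identify only Q4 and Q8 as scales. Q2, Q4, Q6 and Q8 are conditional on a yes, and no denominator is given for them.

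**The case against.** The strongest reply is that the fifth-day gap rests on one footnote against most of the text. Section 5.5.2, the grid, the Day 2-7 copies and the daily reminders all point to daily completion through Day 7. That stands: the footnote is an internal contradiction, not evidence that collection was meant to stop at four days.

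It is also fair that Q5 itself sets no upper time limit. Repeated daily completion would extend coverage, and successive Q6 counts could be differenced. The plan provides for neither.

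Other records of vomiting exist. Safety contacts "on Days 2-7 may occur via in-person visit or telephone call from a study team member", and section 8.1 asks for start and end dates of adverse events. FLIE item 10 asks about vomiting over five days. These are useful cross-checks, but neither is linked to complete response. It is not stated whether continuing CINV, present in every subject at entry, is logged as a new event. The FLIE item is graded, and its timing varies between footnotes 4 and 9.

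A reader might infer that no fifth-day vomiting data will exist, or that complete response cannot be derived at all. The documents do not support that: dated vomiting data may well be collected. A subject would be wrongly counted as a responder through the footnote only if the footnote prevailed, the daily contact missed the event, and the sole failure was vomiting at 96-120 h without rescue. The documents give no basis for estimating how many subjects that would be.

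**Conclusion.** The point holds as a mismatch between form, schedule and endpoint for a secondary outcome. Used as printed, the MAT measures neither promised quantity, and the emesis source and window for complete response are left open. The item description in 5.5.2 and 9.3(3) is wrong for two of the four items called 0-10; that part needs no assumption.

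The size is modest to large, depending on an unstated lag: 0-20% of the window is uncovered with same-day dosing and a single completion of the delayed page, and more with any lag. Under daily completion on Days 2-7 with per-24-hour questions, nothing is uncovered.

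A reader might also infer that one misclassified subject would generally reverse the z test. It would do so only next to a rejection boundary, in practice 40 versus 41 of 50. The primary sample size is unaffected. Because feasibility means completing all study procedures over seven days, the footnote conflict does leave open how many MAT forms a completer must return.

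**What to change.** 1. Reword the post-dose MAT as a daily page on vomiting and nausea in the last 24 hours (on the first form, since taking Akynzeo), with the time of any vomiting. Keep the chemotherapy-timed form for the pre-dose cycle, and make the 'modified' label in 2.2 match Appendix 1.
2. Change footnote 8 to daily completion on Days 2-7, matching 5.5.2 and the grid.
3. Name the daily post-dose MAT in 9.3(2) as the emesis source over 0-120 h after dosing. Use the planned daily contacts to fill missing or undated vomiting, and state which record prevails when they disagree. Keep the Day 7 form in the derivation: with an assumed dose at 15:00 and forms at 09:00, the Day 6 form closes at 5 × 24 − 6 = 114 h.
4. Correct 5.5.2 and 9.3(3) to four yes/no items, two counts and two items scored 0-10 on the printed form. Each daily page, with one set of the same questions, would have two, one and one. Summarise counts as counts (median, IQR, range), and score 'No' as 0 among all completers.
5. Reconcile the Day 1 timing in sections 6.0 and 7.0.

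**Cost.** No new contacts are needed. The form, contact script, case report form and the sections named need small edits. The daily page departs from the original MAT format, so results are less directly comparable with published MAT data, and a second vomiting record needs the precedence rule.

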**Delayed Nausea and Vomiting**

5) Did you vomit 24 hours or more after chemotherapy?      Yes  No   
(Select one)

6) If you vomited during this period, how many times did it happen?        
(Write the number of times in this box)

7) Did you have any nausea 24 hours or more after chemotherapy?      Yes  No   
(Select one)

8) If you had nausea, please circle or enter the number that most closely resembles your experience.  
How much nausea did you have over this time period?

0 1 2 3 4 5 6 7 8 9 10  
None      As much as possible

(Write the number in this box)

Multinational Association of Supportive Care in Cancer™      © 2004 All Rights Reserved      3

---

## **Appendix 2- List of Strong CYP3A4 Inducers and Strong and Moderate CYP3A4 Inhibitors**

### **Strong CYP3A4 inhibitors include the following:**

- Boceprevir
- Clarithromycin
- Conivaptan
- Grapefruit juice
- Indinavir
- Itraconazole
- Ketoconazole
- Lopinavir/ritonavir
- Mibefradil
- Nefazodone
- Nelfinavir
- Posaconazole
- Ritonavir,
- Saquinavir
- Telaprevir
- Telithromycin
- Voriconazole

### **Moderate CYP3A4 inhibitors are the following:**

- Amprenavir
- Aprepitant
- Atazanavir
- Ciprofloxacin
- Darunavir/ritonavir
- Diltiazem
- Erythromycin
- Fluconazole
- Fosamprenavir
- Grapefruit juice
- Imatinib
- verapamil

### **Strong CYP3A4 inducers include the following:**

- Avasimibe
- Carbamazepine
- Phenytoin
- Rifampin
- St. John's wort

**11.2 Appendix 3- Patient Medication Diary**

**Medication Use Diary**

Protocol No.	Participant No.	Participant Initials	Treatment Phase
UCSD XXXXXX			

**Instructions for completion:**

- Please remember to complete this diary **daily** while participating in this study.
- Record each medication you are taking at home on a separate line. For each medication recorded, please list the date or dates that it was taken, how many times it is taken each day, the dose each time it is taken, and the reason why you are taking the medication.
- If there is any information that you do not know, please write "UNK" in the space provided.

Name of Medication	Date(s) Medication Taken (mm/dd/yy)	No. of times taken each day	Dose (each time it is taken)	Reason for Taking Medication

Please sign when all spaces are full and return to the study coordinator during your next clinic visit.

**Patient Signature:** \_\_\_\_\_ **Date:** \_\_\_\_\_

Herbal supplement use?

- No
- Yes, which one? Dose? Frequency? \_\_\_\_\_

Marijuana use?

- No
- Yes, which one? Dose? Frequency? \_\_\_\_\_

[figure not shown]
---

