## **5.0 Description of Procedures**

---

Eligible subjects will be identified in weekly palliative care patient triage meetings. Patients who are 18 years of age or older, have histologically confirmed cancer, and confirmed refractory CINV will be eligible.

After obtaining written informed consent and verifying that the study subject meets all eligibility criteria, the subject will be enrolled in the study through the UCSD Moores Cancer Center Clinical Trials Office. The study coordinator will educate the subject on how to complete the MASCC Antiemesis Tool (MAT), and FLIE scale after CINV prophylaxis. Subjects will be asked to complete the MAT on a daily basis for 4 days and then the FLIE on the 5th day after cancer treatment. Subjects will be allowed to participate only once in the study. Study Day 1 will be the day of Akynzeo® dosing. Subjects will receive a single capsule of Akynzeo® (300 mg of netupitant and 0.5 mg of palonosetron) on Study 1. Study drug may be taken with or without food. Subjects will complete a study drug diary to document date and time of Akynzeo® administration. On Study Day 1, the study coordinator will educate the subject on how to complete the written MASCC Antiemesis Tool, and FLIE scale, and medication diary for each day following the Study Day 1. An adequate number of copies of each subject questionnaire and diary will be provided to the subject on Study Day 1 for completion at home during the post-treatment observation portion of the study (Study Days 2-7) as needed.

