## **5.5 Efficacy Measures:**

### **5.5.1 Patient Medication Diary**

Subjects will be asked to record all oral and self-administered medications received while on study. This will include any rescue medications used to treat their CINV each day, as well as any vitamins, homeopathic/herbal remedies, nutritional supplements, over-the-counter analgesic medication use, and all other over-the-counter "as needed" medications. Subjects will complete this diary (Appendix 3) on the day of Akynzeo® treatment (Study Day 1) and daily during the post-treatment observation portion of the study (Study Days 2-7).

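### Complete response is counted from the capsule, but the medication diary has no clock time, so rescue on Study Day 1 cannot be placed before or after dosing

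*Combined protocol and SAP*

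**What the plan says.** Section 2.2 sets the endpoint: "To evaluate complete response defined as no emesis and no use of rescue medication for 5 days after Akynzeo® administration". Section 9.3(2) analyses it by count and percent, a normal-approximation confidence interval, and a one-sample z test against 90%. It does not say which record supplies the rescue component.

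On the diary:
- Appendix 3 says "Record each medication you are taking at home on a separate line" and, for each drug, "please list the date or dates that it was taken, how many times it is taken each day". Its visible columns are drug name, date(s), times per day, dose and reason. It is to be filled in daily "while participating in this study".
- Section 5.5.1 has a wider scope: "Subjects will be asked to record all oral and self-administered medications received while on study". It includes rescue drugs and covers Study Day 1 and Study Days 2-7.
- Section 5.0 states: "Subjects will complete a study drug diary to document date and time of Akynzeo® administration". No other diary form is appended.
- In the Schedule of Events, the row "Patient medication diary" has one mark, under Study Day 1. Footnote 5 provides daily reminders on Days 2-7 that cover diaries.

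Other relevant provisions:
- Section 5.4 permits routine prophylaxis and routine breakthrough drugs during the study week.
- Section 6.0 has the capsule taken once the other Day 1 procedures are done.
- The Schedule marks concomitant medications in all four columns.
- Section 5.5.4 asks daily about emergency, hospital and infusion visits and requests records of outside visits.

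**The concern.** The endpoint window opens at a moment, the swallowing of the capsule, but the rescue record resolves only to the calendar day. A dopamine antagonist or benzodiazepine taken on the morning of Study Day 1 and one taken that evening look the same on the form, although only the one after the capsule counts against response.

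The analyst then has two conventions, each wrong for some patients. Counting all Day 1 use as failure turns patients who took rescue only before dosing into non-responders. Ignoring Day 1 use turns patients who failed within hours of dosing into responders. No section chooses between them, and an analyst cannot supply times that were not written down.

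A second gap concerns rescue given by staff at a facility. It is outside a diary limited to home or self-administered drugs, and no section says that the concomitant-medication or visit records feed the endpoint.

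Complete response is the only secondary outcome with a named hypothesis test, and Section 5.3 intends the secondary results to guide the endpoint of a larger study.

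**Working it through.** **1. The plan's own figure.** The only sizing statement is for the primary endpoint (Section 9.2): 85% against 70% completion, N=50, Type I error 0.05, power 80%. With a one-sided normal approximation:

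Φ[(0.15×√50 − 1.645×√(0.70×0.30)) / √(0.85×0.15)] = Φ[(1.061 − 0.754)/0.357] = Φ(0.86) = 80.5%.

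This reproduces, and it does not involve the diary. Complete response has no sizing statement.

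**2. What a date alone can settle.**
- Study Day 1: not settled. The capsule falls within the day, and breakthrough drugs are allowed on either side of it.
- Study Days 2-5: settled. Any rescue on these dates is after the capsule and inside the window.
- End of window: depends on how 5 days is read. In calendar days with Day 1 as the first, the window closes with Study Day 5 and the date is enough. Counted from dosing time, five 24-hour periods end part-way through Study Day 6, and the date is not enough. Section 2.2 does not say which is meant.

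**3. Illustrative size.** The documents give neither an expected response rate in this population nor a rate of same-day rescue. The following are assumptions: true rate p from 30% to 70%, affected share f from 5% to 20%, N=50.

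(A) A share f of true responders took rescue before the capsule on Day 1 and is counted as failures: observed = p(1 − f).

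(B) A share f of non-responders failed only through rescue that is not counted, because Day 1 is ignored or the drug was given at a facility: observed = p + (1 − p)f.

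Half-width of the 95% confidence interval: 1.96×√(p(1 − p)/50).

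| True rate | f | (A) reads as | (B) reads as | Half-width, points |
|---|---|---|---|---|
| 30% | 5% / 20% | 28.5% / 24% | 33.5% / 44% | 12.7 |
| 50% | 5% / 10% / 20% | 47.5% / 45% / 40% | 52.5% / 55% / 60% | 13.9 |
| 70% | 5% / 20% | 66.5% / 56% | 71.5% / 76% | 12.7 |

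The shift runs from 1.5 points (0.30×0.05) to 14 points (0.70×0.20) in each direction. Each misclassified patient moves the rate by 1/50 = 2 points.

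**4. Effect on the test against 90%.** z = (observed − 0.90)/√(0.90×0.10/50). At 50% observed, z = −9.43; at 40%, z = −11.79; the conclusion is the same. Near 90% it can change: 45/50 gives z = 0 and 40/50 gives z = −2.36, a difference of five patients. Away from 90%, what suffers is the estimate, not the test result.

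**The case against.** The case on the other side is substantial, and most of it limits the point without removing it.

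- **Diary days.** A reader might infer from the single Schedule mark that rescue on Days 2-5 goes uncollected. The documents do not support that. Section 5.5.1 requires the diary through Day 7, Appendix 3 says daily, Section 5.0 supplies copies for home use, and both Section 5.1 and Schedule footnote 5 provide daily reminders. The mark may show when the form is handed out, or a merged cell may have been lost in reading the table. It is an inconsistency to correct.
- **Facility-given rescue.** Concomitant medications are recorded throughout and visits are followed up, so such rescue has a possible source. Nothing says that complete response is taken from the diary alone. What stands is that no source is named and no rule combines them; Section 5.5.4 as written also collects visits, symptoms and reasons, not the drugs given.
- **Frequency of pre-capsule rescue.** A reader might infer from the entry criterion that rescue earlier on Study Day 1 is the usual case. The criterion requires previous first-line rescue but does not place it on Study Day 1. Such use is possible, since Section 5.4 permits it, but its rate is unknown.
- **Window end.** A fixed 120-hour limit is tempting, but Section 2.2 speaks only of days.
- **Form not fully visible.** Appendix 3 ends in a figure that is not shown, and Section 5.0 speaks of a study drug diary, which might be a separate form. An unseen field for the capsule's time cannot be excluded. The written instructions to patients, however, list what to record for each drug, and time is not among the items.

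**Conclusion.** The point holds in a limited form. From the diary as it can be read, rescue on Study Day 1 cannot be placed relative to the capsule, and the end of the window is ambiguous if the 5 days run from dosing time. Patients may be misclassified there, and also where rescue was given at a facility. It does not follow that they will be, or that Days 2-5 are affected.

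The errors run in opposite directions, so the net bias is unknown in sign and size. Under the assumed shares it is small beside sampling error at 5% and, at 20%, ranges from about half the interval half-width to slightly more than the whole of it. Those shares are for scale only and have no source in the documents.

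Complete response is secondary and the feasibility sizing stands. A change is still justified because it is cheap and because missing intake times cannot be reliably reconstructed at analysis.

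**What to change.** 1. In Appendix 3, add a time-taken field for the Akynzeo capsule and for each antiemetic. This also supplies the record that Section 5.0 promises.
2. In Section 9.3(2), state that the rescue component counts antiemetics given for nausea or vomiting after capsule time, drawn from the diary together with the concomitant-medication record and the Section 5.5.4 visit records. Exclude the routine scheduled prophylaxis that Section 5.4 permits; otherwise the wider definition would create false failures. Say whether the 5 days are calendar days or run from dosing time.
3. Reconcile the diary row of the Schedule of Events with the Days 1-7 required by Section 5.5.1.

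The cost is one diary field, one Schedule correction and a short addition to Section 9.3, with slight extra patient burden. The reported response rate may fall slightly where facility-given rescue is counted. The sample size does not change.
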